HRP-503B – BIOMEDICAL RESEARCH PROTOCOL
(2017-1)

Protocol Title: Mechanisms for restoration of hypoglycemia awareness

Principal Investigator: [name], MD

Version Date: August 2, 2022

Clinicaltrials.gov Registration #: NCT03738852

SECTION I: RESEARCH PLAN

1. **Statement of Purpose:** State the scientific aim(s) of the study, or the hypotheses to be tested.

Aim 1: Determine the impact of frequent hypoglycemia and hypoglycemia unawareness on brain responses to visual food cues as well as brain functional connectivity in T1DM patients.

Aim 2: Assess the impact of antecedent bouts of hypoglycemia on brain glucose transport/metabolism during hyperglycemia in T1DM Unaware, T1DM Aware as well as healthy controls using ¹H, ¹³C magnetic resonance spectroscopy (MRS).

Aim 3: Determine if reducing hypoglycemia and glycemic variability using a continuous glucose monitor (CGM) reverses altered brain glucose transport/metabolism and functional connectivity in hypoglycemia unaware T1DM patients.

Optional Sub Study: Assess the impact COVID-19 pandemic and related shutdown has had on the management of diabetes amongst patients with T1DM.
2. **Probable Duration of Project:** State the expected duration of the project, including all follow-up and data analysis activities.

5 years
3. **Background:** Describe the background information that led to the plan for this project. Provide references to support the expectation of obtaining useful scientific data.

The DCCT and EDIC trials established the benefits lowering blood glucose to “near normal” levels in type 1 diabetes (T1DM) patients ¹⁻³. This has led to the widespread use of more intensified insulin therapy to prevent or delay diabetes complications. However, global application of intensive insulin therapy has been limited by a higher rate of severe hypoglycemia, often occurring without warning symptoms and thus reducing the patient’s ability to take corrective action ⁴. As a result, many patients do not and/or become afraid to achieve target glycemic goals, since their immediate fear of hypoglycemia exceeds their fear of future long-term complications ^{5,6}. In non-diabetic subjects, hypoglycemia provokes a multi-tiered defense system including: 1) suppression of

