- a. Food Cues: Picture stimuli for fMRI are high-calorie/high carbohydrate food, and non-food neutral pictures selected from Web sites and from the International Affective Picture System.
- b. Cognitive tasks: include tasks to assess working memory (N-Back), attention (Grad-CPT) and reward (Card guess) that have been adapted for the MRI setting. In order for these tasks to be as accurate as possible, the subjects will need to think that they will get a monetary bonus depending on how they do. In reality, all subjects will "win" and get this bonus.

Aim 2: The same 3 subject groups who participated in Aim 1 will participate in Aim 2. As previously stated, for ease of scheduling, this visit may precede the fMRI visit discussed above.

1. 1H-[13C] MRS scanning and Hyperglycemic Clamp: Participants will arrive at MRRC at 7AM on the morning of the study after an 8 hour overnight fast. A urine pregnancy test will be performed on all women of childbearing potential, and women who are pregnant will be excluded. Following IV placements and baseline blood collection, at ~8 AM all T1DM subjects will receive a low dose insulin infusion to prevent ketosis during the MRS study and a variable glucose infusion to keep plasma glucose levels at ~100-110 mg/dl. Once glucose levels are stabilized, the subjects will be transferred into the 4T

scanner (¹³C ¹H for POCE) for the hyperglycemia clamp with labeled glucose. At the start of the study, plasma glucose will be increased to ~180 mg/dl by a primed continuous infusion of 99% 1-¹³C glucose (Cambridge Isotope Lab) (dextrose 1.1 M) and will be maintained at ~180 mg/dl throughout the study with a variable infusion of 60% ¹³C glucose (dextrose 1.1 M). Plasma glucose will be measured every 5 min. Throughout, blood will be obtained for insulin, fructose, sorbitol, ¹³C enrichment and other hormonal and metabolic blood tests. A1c will also be measured at this visit. After tuning, calibration, and acquisition of scout images for anatomical localization, metabolite concentrations will be obtained from 18 ml³ voxel. Using metabolic modeling we will determine rates of glucose uptake, TCA cycle (VTCA) and glutamate/glutamine cycling (Vcycle) as well as measure absolute glucose and fructose levels and ¹³C labeling.

Aim 3: T1DM-UA subjects that completed Aims 1 and 2 will participate in Aim 3.

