Data analysis will be conducted in collaboration with [name] at the Yale Center for Analytic Sciences. For Aim 1, we will require 25 T1DM aware and 25 healthy controls to provide 80% power to detect differences of 0.013 between them and the T1DM-Unaware subjects at the Bonferroni corrected 0.017 significance level. This sample size will also provide 80% power at the 0.01 level of significance to detect a difference of 0.22 for average brain glucose for Aim 2. We will enroll 27 aware and 27 healthy controls to accommodate a potential

5% inadequate scan rate. The T1DM Unaware group sample size (n=40) was first determined to provide sufficient power for Aim 3. T1DM Aware and healthy control sample sizes were then estimated based on power for aims 1 and 2. Our preliminary data shows differences in the co-primary outcome of average brain glucose between those with a low glucose variability index and those with a high glucose variability index of 0.455 (SD=0.26). We've also observed a difference of 0.013 (SD=0.016) in our other co-primary outcome change in brain activity from hypoglycemia to euglycemia in the striatum between T1DM Aware and Unaware. Thus, for Aim 3 a sample size of 20 T1DM Unaware subjects per arm will provide 80% power to detect a difference of 0.22 in brain glucose and 0.013 in change in brain activity. We will enroll 65 Unaware for Aim 3 in order to accommodate a potential 10% dropout rate.

Aim 1 Analysis: Comparison of brain activity between groups will be performed using a repeated measures mixed model. The outcome will be brain activity in our primary region of interest, the caudate region of the striatum. Fixed factors for group (unaware, aware, HC), glucose category (eugly, mild hypo, moderate hypo) and their interaction will be included. Linear contrasts comparing changes in brain activation from euglycemia to moderate hypo between groups will be estimated and evaluated at the 0.017 Bonferroni corrected significance level. Secondary analyses will examine other promising ROIs (hypothalamus and prefrontal cortex). Similar analyses will be done to assess group differences in resting state connectivity and hormones.

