Aim 2 Analysis: Comparisons of glucose levels in specific brain regions will be made using a repeated measures mixed model. Fixed factors include group and glycemic state (e.g. acute hyperglycemia) and their interaction. A random effect for subject will be used to accommodate correlation between repeated assessments. Linear contrasts comparing differences in average brain glucose between groups will be estimated. A significance level of 0.01 will be used to accommodate multiple pairwise comparisons of groups. Similar secondary analyses will be conducted to assess differences in V_{TCA} between groups and fructose production during hyperglycemia. For the rodent studies our preliminary data showed a 1.5 standardized difference in fructose and glutathione concentrations between groups, so a sample size of 14-15 rats per group will provide 80% power to detect a large standardized difference in study outcomes at the two-sided 0.05 significance level. Between-group comparisons, ANOVA and t-tests will be used for continuous variables, where applicable.

Plan for Missing Data: Prevention is the obvious way to control for bias and loss of power from missing data (71). We will follow the intent to treat principle, requiring follow-up of all subjects regardless of treatment³⁴. Postcard and telephone visit reminders will be sent and alternative contacts identified to minimize loss to follow-up. Timely data entry and weekly missing data reports will trigger protocols for obtaining missing data items. Despite these efforts it is reasonable to assume missing data will occur most likely at random³⁵. We will evaluate the plausibility of this assumption using logistic regression to identify factors linked to dropout.

SECTION II: RESEARCH INVOLVING DRUGS, BIOLOGICS, RADIOTRACERS, PLACEBOS AND DEVICES

If this section (or one of its parts, A or B) is not applicable, check off N/A and delete the rest of the section.

A. RADIOTRACERS N/A

B. DRUGS/BIOLOGICS N/A

1. Use of Placebo: Not applicable to this research project

2. Continuation of Drug Therapy After Study Closure Not applicable to this project

B. DEVICES N/A

1. Are there any investigational devices used or investigational procedures performed at Yale-New Haven Hospital (YNHH) (e.g., in the YNHH Operating Room or YNHH Heart and Vascular Center)? Yes No

If Yes, please be aware of the following requirements:

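### The Aim 2 contrast of average brain glucose gives no role to the plasma glucose achieved during the scan, so any clamp difference between groups would read as a brain glucose difference

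*Combined protocol and SAP*

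**What the plan says.** The Statement of Purpose words Aim 2 as "Assess the impact of antecedent bouts of hypoglycemia on brain glucose transport/metabolism during hyperglycemia". The Research Plan (Aim 2, item 1) describes one hyperglycemic clamp, aimed at about 180 mg/dl and held there by a variable glucose infusion, with no tolerance band. During it, "Plasma glucose will be measured every 5 min". On insulin, the same item says that "all T1DM subjects will receive a low dose insulin infusion to prevent ketosis during the MRS study"; it states none for healthy controls. It also plans metabolic modelling of glucose uptake, the TCA cycle rate and glutamate/glutamine cycling.

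Section I, 13 makes average brain glucose a co-primary outcome. On power it says: "This sample size will also provide 80% power at the 0.01 level of significance to detect a difference of 0.22 for average brain glucose". The Aim 2 Analysis paragraph lists group, glycemic state and their interaction as fixed factors, with a random subject effect, and then: "Linear contrasts comparing differences in average brain glucose between groups will be estimated". It sets the level at 0.01 for the pairwise group comparisons and adds similar secondary analyses of the TCA cycle rate and fructose production. It names no plasma glucose covariate, brain-to-plasma ratio or check of clamp balance between groups, and it does not assign the modelled uptake rate to any comparison.

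**The concern.** Brain glucose depends on the plasma glucose that supplies it. The plan recognises this by making glycemic state a model factor. A category, however, cannot absorb variation within the state: subjects held at 172 and at 188 mg/dl would both count as hyperglycemic. If one group settles a little higher than another, the raw contrast cannot separate altered transport from a different supply.

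The route to imbalance differs by contrast. For T1DM versus controls there is a possible systematic reason, since only the T1DM groups have a stated insulin infusion while controls keep their own insulin response. Unaware and Aware subjects share the same stated procedure, so a gap between them would arise by chance, and clamp variation would otherwise act as noise.

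At stake is how a co-primary result is read. A clamp gap could create an apparent difference or hide a real one. With no adjustment specified in advance, the choice between raw and adjusted results would be made after the data are seen.

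**Working it through.** **Inputs from Section I, 13.** Target difference 0.22; SD 0.26 (from the preliminary comparison of low and high glucose variability; no SD is given for the Aim 2 groups); level 0.01; 25 Aware, 25 controls, 40 Unaware. Sidedness is not stated for the human comparisons; two-sided is assumed.

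**The plan's own figure.** For 40 versus 25:

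SE = 0.26 × √(1/25 + 1/40) = 0.0663, and 0.22 / 0.0663 = 3.32.

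Power at two-sided 0.01 is 77.1% (normal) or 74.4% (noncentral t), against the stated 80%. With the 27 planned for enrolment and no scan loss it is 79.4% or 76.9%. This shortfall is a separate matter, and the present point does not depend on it.

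**Effect of a shift, with no slope assumed.** Suppose two groups have equal transport, but a clamp gap shifts the contrast by b. The rejection rate is the two-sided noncentral t probability with 63 df and noncentrality b / 0.0663:

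| b | Rejection rate (nominal 1%) |
|---|---|
| 0.05 | 3.3% |
| 0.10 | 13% |
| 0.15 | 35% |

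**From mg/dl to b (assumptions not in the documents).** Brain glucose is taken to be in mmol/L, rising 0.1 to 0.3 mmol/L per mmol/L of plasma. The gaps of 5 and 10 mg/dl are also only illustrations. Then b = (gap / 18.016) × slope.

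| Gap | mmol/L | Slope | b | Share of 0.22 | Rejection rate, 25 vs 40 |
|---|---|---|---|---|---|
| 5 mg/dl | 0.278 | 0.1 | 0.028 | 13% | 1.7% |
| 5 mg/dl | 0.278 | 0.3 | 0.083 | 38% | 8.8% |
| 10 mg/dl | 0.555 | 0.1 | 0.056 | 25% | 4.0% |
| 10 mg/dl | 0.555 | 0.3 | 0.167 | 76% | 45% |

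For Aware versus controls (25 versus 25, SE 0.0735) the ranges are 1.5-6.9% at 5 mg/dl and 3.3-35% at 10 mg/dl. A gap that produced the whole 0.22 would be 0.22 / 0.3 × 18.016 = 13 mg/dl at the steep slope and 0.22 / 0.1 × 18.016 = 40 mg/dl at the shallow one. If the gap runs against a true difference of 0.22, a 10 mg/dl gap cuts t-based power for 25 versus 40 from 74% to between 44% and 4%.

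These rates are conditional on the gap. For a systematic gap they are the long-run error rate. Clamp variation unrelated to group leaves the long-run rate at 1%; it adds outcome variance, and can mislead in the one trial where a chance imbalance occurs.

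**After adjustment.** With a linear relation and a common slope, the covariate removes b. Residual SD is 0.26 × √(1 − ρ²), where ρ is the within-group brain-plasma correlation (not given). With one df lost, t-based power for 0.22 at 25 versus 40 is 74% at ρ = 0, 79% at ρ = 0.3 and 88% at ρ = 0.5.

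**The case against.** The strongest reply is that this is a feedback clamp. Glucose is read every 5 minutes and the infusion is varied to hold the target, so different insulin physiology should mainly change the infusion rate needed and leave the plateau alone. That stands as a reason why a gap may be small or absent. It does not show that the clamp will succeed equally in all groups, and the plan includes no check that it did.

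Four stronger readings are tempting, and the documents do not support them.

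- A reader might infer that plateaus will differ systematically between groups. The text says the T1DM insulin is low dose; it does not say that it is fixed, and no group gap is documented. The argument from insulin also reaches only the contrasts with controls.
- A reader might infer that Aim 2 rests on raw brain glucose alone. The plan also models uptake, and it compares the TCA cycle rate and fructose production. What remains is that uptake, the measure closest to transport, is assigned to no comparison.
- A reader might infer that the model excludes all covariates. The wording of the factor list is not strictly exhaustive. Still, no plasma covariate is named.
- A reader might infer a biased week-12 change in Aim 3. The same subjects repeat the same procedure, which gives a reason for random drift between scans but none for a systematic shift.

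It is also fair to object that one common slope assumes brain glucose responds to plasma equally in all groups, when a transport difference could itself alter that slope. The sensitivity check below addresses this.

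**Conclusion.** The omission is real and worth correcting. The stated Aim 2 model would pass any difference in achieved plasma glucose straight into a co-primary contrast, while the readings needed to prevent this are already taken. Whether the bias would be material cannot be settled from the documents: it depends on a gap they do not show and on units and a slope they do not give. Over the assumed slope range the effect runs from negligible (about 2% against a nominal 1%, at 5 mg/dl and the shallow slope) to serious (about 45%, at 10 mg/dl and the steep slope). The case for change rests on the low cost of prespecifying the adjustment, and is strongest for T1DM versus controls. For Unaware versus Aware the expected gain is mainly less noise and protection against chance imbalance.

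**What to change.** In the Aim 2 Analysis:

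1. Add each subject's mean plasma glucose over the MRS acquisition window as a covariate. Centre it within glycemic state, on a value common to all groups. Centring at 180 mg/dl throughout would make it nearly collinear with glycemic state if more than one state is modelled; centring on each group's own mean would leave the gap in the contrast.
2. Add a group-by-plasma-glucose interaction as a sensitivity check on the common slope.
3. Report achieved plasma glucose by group beside the contrast, and give the brain-to-plasma glucose ratio as a supporting outcome.
4. Assign the modelled glucose uptake rate to a named group comparison.

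Section I, 13 has no Aim 3 analysis paragraph. When one is written, it should use the same covariate for the week-12 brain glucose comparison.

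The cost is a few sentences and one variable derived from readings already planned, with no new samples. The primary model loses one degree of freedom and the sensitivity check uses more. The adjusted contrast assumes linearity and a common slope.

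### Aim 2 tests the same three group pairs as Aim 1 at an unexplained 0.01 instead of 0.05/3, which takes its power below the stated 80%; a three-group step-down rule would do better in both aims

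*Combined protocol and SAP*

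**What the plan says.** All of this is in Section I, 13 (Statistical Considerations), unless noted.

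- **Groups.** The Aim 1 model states: "Fixed factors for group (unaware, aware, HC), glucose category (eugly, mild hypo, moderate hypo) and their interaction will be included". Section I, 4 (Research Plan, Aim 2) states: "The same 3 subject groups who participated in Aim 1 will participate in Aim 2".
- **Aim 1 level.** Contrasts between groups in the change from euglycemia to moderate hypoglycemia "will be estimated and evaluated at the 0.017 Bonferroni corrected significance level".
- **Aim 2 level.** "Linear contrasts comparing differences in average brain glucose between groups will be estimated", followed by: "A significance level of 0.01 will be used to accommodate multiple pairwise comparisons of groups".
- **Planning.** For Aim 1, "we will require 25 T1DM aware and 25 healthy controls to provide 80% power" for a difference of 0.013 from the Unaware group at 0.017. The same numbers are said to give 80% power at 0.01 for a difference of 0.22 in average brain glucose (Aim 2). The Unaware group is fixed at 40.

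Brain glucose and striatal activity are called co-primary outcomes. No step-down rule, overall test or adjustment across the two outcomes is described.

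**The concern.** Three groups give three pairs. Bonferroni at 5% is then 0.05/3 = 0.0167, which Aim 1 rounds to 0.017. Aim 2 gives the same purpose for its adjustment but uses 0.01, which spends only 3 x 0.01 = 0.03. That is the Bonferroni level for five comparisons (0.05/5), and no set of five is described. If only the two contrasts against Unaware were meant, the level would be 0.05/2 = 0.025 and 0.01 would be stricter still.

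Two things are at stake. The first is whether Aim 2 has the power it claims on a co-primary outcome. The second is whether a single-step rule is the best choice with exactly three groups. If any two pairwise equalities hold, the third must hold too. So once one equality has been rejected, at most one of the remaining two can be true, and both can be tested at 0.05 without exceeding 5% within the aim (Shaffer's form of Holm).

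**Working it through.** **Inputs from Section I, 13.** Sizes: Unaware 40, Aware 25, controls 25. Aim 1: difference 0.013, SD 0.016. Aim 2: difference 0.22, SD 0.26. That SD is quoted for a comparison of low and high glucose variability, so its use for awareness groups is an assumption. Two-sided testing is also assumed: the plan states it only for the rodent studies ("at the two-sided 0.05 significance level").

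**Step 1: the plan's own power.** SE = SD x sqrt(1/25 + 1/40) = SD x 0.2550. Normal-approximation power = Phi(difference/SE - z), where z is 2.387 at 0.017, 2.394 at 0.05/3 and 2.576 at 0.01. The t figures use the noncentral t with 63 df.

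- Aim 1 at 0.017: SE = 0.00408; 0.013/0.00408 = 3.187; Phi(3.187 - 2.387) = 78.8% (t: 76.7%). This is close to the stated 80%.
- Aim 2 at 0.01: SE = 0.0663; 0.22/0.0663 = 3.319; Phi(3.319 - 2.576) = 77.1% (t: 74.4%). The stated 80% is not reached. The difference detectable with 80% power is (2.576 + 0.842) x 0.0663 = 0.227. With Unaware held at 40, the other groups would need 28 each (30 by t).
- Aim 2 at 0.05/3: Phi(3.319 - 2.394) = 82.2% (t: 80.2%). The stated 80% is reached.

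**Step 2: sensitivity to the assumed Aim 2 SD** (same formula; t figure, then normal).

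| SD | at 0.01 | at 0.05/3 |
|---|---|---|
| 0.24 | 82%, 85% | 87%, 88% |
| 0.26 | 74%, 77% | 80%, 82% |
| 0.28 | 66%, 69% | 73%, 75% |

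**Step 3: step-down.** Simulation with 400,000 trials per scenario, sizes 40/25/25, normal data and pooled variance on 87 df. Unaware differs from both other groups by the planned effect, and Aware equals controls.

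| | Per Unaware contrast | Both Unaware contrasts |
|---|---|---|
| Aim 1, single-step 0.017 | 77% | 64% |
| Aim 1, step-down | 84% | 78% |
| Aim 2, single-step 0.01 | 75% | 61% |
| Aim 2, single-step 0.05/3 | 81% | 69% |
| Aim 2, step-down | 87.5% | 82% |

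**Step 4: other patterns of means.** With controls midway between Unaware and Aware, the largest Aim 1 contrast goes from 77% to 78-79%, a gain of about 1 point. The two smaller contrasts gain about 12 points (21% to 33% and 17% to 29%). The chance of at least one rejection in Aim 1 does not improve: in the Step 3 scenario it is 90.7% at 0.017 and 90.6% with step-down, a difference due only to rounding 0.05/3 up.

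**Step 5: error.** Under the global null, the familywise error is 4.4% in Aim 1 and 2.7% in Aim 2 as planned, and 4.3% with step-down. When Unaware differs and Aware equals controls, false rejection of Aware versus controls is 1.7% at 0.017, 1.0% at 0.01 and 5.0% with step-down. Across the two co-primary outcomes the Bonferroni bound is now 3 x 0.017 + 3 x 0.01 = 0.081. With 5% spent in each aim it becomes 0.10.

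**The case against.** The plan is valid as it stands. Single-step Bonferroni is prespecified and conservative, and choosing it is defensible. A reader might infer from the mismatched levels that error is not controlled. The documents do not support that: Aim 1's nominal sum of 3 x 0.017 = 0.051 is a rounding effect, and its actual error is 4.4%.

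A reader might also infer that the step-down gain is free. It is not. The extra power uses error that the present plan leaves unspent, as Step 5 shows. The 5% holds only within each aim, and the co-primary bound rises. Nor does step-down produce all of the Aim 2 gain: of about 12 points, nearly half (75% to 81%) comes simply from leaving 0.01. The gain also shrinks when one group lies between the other two.

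Perhaps 0.01 was meant to cover more than three comparisons. The Aim 2 paragraph mentions several brain regions and a group-by-state interaction, and does not count its contrasts. That uncertainty stands, and it is why the rule below is limited to one primary contrast set per aim. But the only reason the plan gives for 0.01 is pairwise comparison of groups. It mentions neither regions nor protection across co-primary outcomes.

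Finally, the sub-study text refers to participants already enrolled in Aims 1 and 2. Relaxing a threshold after group comparisons have been seen would not be credible. That objection stands as a condition on the change.

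**Conclusion.** The concern holds as an inconsistency in Aim 2 and a cheap gain in efficiency, not as a failure of error control. The 0.01 is stricter than three pairwise comparisons need. On the plan's own figures it leaves Aim 2 at 74-77% power against a stated 80%, whereas 0.05/3 gives 80-82%. Step-down adds about 7 points per Unaware contrast in each aim beyond single-step 0.05/3 if Unaware differs from both other groups, and much less for the largest contrast under a graded pattern.

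These figures assume three contrasts per aim (inferred from three groups and 0.05/3), two-sided tests, equal SDs, and 0.016 and 0.26 as the SDs of the contrasts analyzed. The Aim 2 shortfall is sensitive to the last: at an SD of 0.24 the stated 80% would be met even at 0.01.

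**What to change.** **Minimum.** In the Aim 2 analysis replace 0.01 with 0.05/3, as in Aim 1, and restate the Aim 2 planning level and power to match. If 0.01 is kept, give the reason and correct the stated power or the group sizes.

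**Preferred.** In both aims replace the fixed level with wording such as: *For the primary contrast set (Aim 1: caudate change from euglycemia to moderate hypoglycemia; Aim 2: average brain glucose), the three pairwise p-values are ordered. The smallest is tested at 0.05/3, two-sided. If it is significant, each of the other two is tested at 0.05.* State that other regions and outcomes are secondary and fall outside this rule.

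**If one overall 5% is wanted across the co-primary outcomes,** split alpha first and apply the rule within each share. An equal split gives 0.025 per aim: the smallest p-value at 0.025/3 = 0.0083, then the others at 0.025. Power must then be recalculated.

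**Cost.** A few sentences in Section I, 13, with no new subjects, visits or data. The full 5% is spent in each aim, and confidence intervals are no longer simultaneous, so report them unadjusted and label them so. The amendment should be dated before any group comparison is examined and should say so.
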